In anticipation of this protocol, we have pilot-tested the curriculum at three affiliated institutions with general surgery residents at varying levels of training. Focus group data was collected to garner feedback on the effectiveness and feasibility of the curriculum. **The purpose of the current protocol is to implement the curriculum across eight institutions and measure resident-level competency outcomes, as well as patient-reported and clinical outcomes, following this training.**

RESEARCH DESIGN AND METHODS

Briefly describe study design and anticipated enrollment, i.e., number of subjects to be enrolled by researchers study-wide and by Partners researchers. Provide a brief summary of the eligibility criteria (for example, age range, gender, medical condition). Include any local site restrictions, for example, "Enrollment at Partners will be limited to adults although the sponsor's protocol is open to both children and adults."

We will conduct a cross-over, cluster-randomized trial at 8 academic medical centers (AMCs) to capture the effect of PACTS on: 1) resident knowledge and attitudes regarding cross-cultural health care [Specific Aim (SA)1], 2) interpersonal and communication skills in simulated patient-clinician encounters [SA2], and 3) patient-reported satisfaction with resident physicians involved in their care, and clinical outcomes [SA3]. Sites will be assigned to an early intervention/retention assessment group or a control group with delayed intervention for examination of the effectiveness of the intervention as well as learner retention. After cluster-randomization, we will assess the residents' knowledge, attitudes, and skills prior to and after the PACTS curriculum at half the sites (Early Intervention/Retention Group). We plan to conduct follow-up testing after one year to evaluate learner retention.

At the other sites (Delayed Intervention Group), we will conduct baseline testing prior to the standard residency curriculum, and administer the PACTS curriculum the following year. This study design will enable us to examine both between- and within-group differences based on curriculum exposure in intervention year 1 as well as within-group differences for the Delayed Intervention Group at the end of year 2. Further, we will also be able to test post-exposure effect retention in the Early Intervention Group at the end of year 2.

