To evaluate the impact of PACTS on surgical residents' knowledge and attitudes about caring for diverse patients, we will use a pre- and post-test in the form of validated instruments that assess knowledge, attitudes, and self-reported skills on a Likert-type scale. This pre- and post-test will be piloted among a group of surgical residents (N=40) to assess the survey length and clarity of questions. Residents will be recruited using a convenience sampling method from those who participated in the surgery focus groups at ASC 2019. Exclusion criteria from this pilot will be residents at one of the trial AMCs.

Resident skills will also be objectively assessed through an Objective Structured Clinical Examination (OSCE) that will be created by the study

staff and administered immediately before the intervention and within 1-6 months after the intervention has been completed. The OSCE uses 5-point Likert scale questions to evaluate resident performance across multiple domains. A Standardized Patient evaluator and a third-party trained impartial observer will evaluate the residents on these domains, and the resulting numerical scores will be averaged. It will serve both a summative and educational purpose in this context. Due to the COVID-19 pandemic, in order to adhere to social distancing protocols, the OSCE may also be delivered virtually using a secured web-based video-conference software.

We have also developed a novel survey instrument to assess resident knowledge, attitudes, and self-reported skills. This instrument is adapted from pre-existing, validated instruments such as the Cultural Competence Health Practitioner Assessment (CCHPA), developed by the National Center for Cultural Competence, and modified to be relevant to surgical training and practice. Residents will be required to take a knowledge survey before and after receiving the PACTS curriculum or standard training. Attitudes regarding the importance of facing cross-cultural health care situations will be assessed across multiple domains using a novel survey instrument that is based on a survey that was used in a similar curriculum aimed at medical students, as well as the Values and Belief Systems domain.

Patients

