All general surgery residents will receive the educational curriculum; each site's Program Director (PD) has agreed to schedule PACTS training during compulsory didactic sessions, when residents are free from clinical duties. However, participation in study assessments (OSCEs and knowledge-testing) is voluntary and will not impact residents' performance in their program. Final analyses will include enrolled residents regardless of their attendance in live modules, reflecting an "intention-to-treat" analysis approach. This will more accurately demonstrate the "real world" benefit of PACTS, as not all residents may be able or willing to attend all live sessions. Based on the size of the residency programs, which ranges between 46 and 72 residents, and the away rotation schedules, we expect to enroll 200 residents per arm for analysis (an average of 50 residents per site).

Patient Recruitment

At the onset of clinical rotations, the Program Manager will contact surgical residency Program Coordinators to attain general surgery resident rotation schedules. The Program Manager will identify the dates and times of resident study participants' rotations. On these dates and times, Research Assistants working under the supervision of the Program Manager will verify that the resident is on rotation and use the EHR at the surgical service site to

randomly select at least two eligible patients from the EHR. First, the RA will approach the patients' nurse and ask whether the nurse might have a concern regarding the selected patients' cognitive status. If the nurse has no concerns, the nurse will be asked to introduce study staff to the patient. Staff will provide an information sheet, describe the study, and ask them to identify a resident participating in the PACTS trial who they recall interacting with. The RA will explain the study and provide the patient with a copy of the Patient Information Sheet and survey, which will be administered via tablet or laptop computer to access the survey in the Partners-hosted REDCap database. Completion of the English or Spanish language survey will indicate consent to participate in the study and the patient will be enrolled.

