[https://partnershealthcare-public.sharepoint.com/ClinicalResearch/Guidelines For Advertisements.1.11.pdf](https://partnershealthcare-public.sharepoint.com/ClinicalResearch/Guidelines%20For%20Advertisements.1.11.pdf)

Remuneration for Research Subjects

[https://partnershealthcare-public.sharepoint.com/ClinicalResearch/Remuneration for Research Subjects.pdf](https://partnershealthcare-public.sharepoint.com/ClinicalResearch/Remuneration%20for%20Research%20Subjects.pdf)

CONSENT PROCEDURES

Explain in detail how, when, where, and by whom consent is obtained, and the timing of consent (i.e., how long subjects will be given to consider participation). For most studies involving more than minimal risk and all studies involving investigational drugs/devices, a licensed physician investigator must obtain informed consent. When subjects are to be enrolled from among the investigators' own patients, describe how the potential for coercion will be avoided.

Focus Groups

Participants will be provided a fact sheet that contains information regarding the focus group that they will be participating in. Consent will be indicated either through completion of an online registration form or through participation in the focus group.

Survey Pilots

Participants will be provided with a fact sheet that contains information regarding the survey pilot. Consent will be indicated through voluntary completion of the survey.

Residents

Each program director will initiate recruitment for their site and provide email contacts, but a research assistant will enroll and consent residents. Following the didactic curriculum and prior to the first testing sessions, residents will review an informational sheet that they may keep for reference. Completing the resident surveys will indicate consent to participate in the study. Prospective subjects will be reminded that their decision to enroll in the study will remain confidential, as will their performance evaluations if they choose to participate. De-identified informed

consent documents will be maintained by the research assistant in a locked folder on-site or on a protected and secure database.

Patients

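### Residents are baseline-tested, and by that act enrolled, after their site is randomised, with nothing withholding the arm, so who joins and how they answer the self-reported baseline can depend on the arm

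*Protocol*

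**What the plan says.** **Order of events.** Research Design and Methods in the Protocol states that "After cluster-randomization, we will assess the residents' knowledge, attitudes, and skills prior to and after the PACTS curriculum at half the sites". For the Delayed sites it says "we will conduct baseline testing prior to the standard residency curriculum, and administer the PACTS curriculum the following year". In both arms the baseline is taken once the site's assignment exists.

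**Enrolment.** Under Recruitment Procedures (Resident Recruitment), "participation in study assessments (OSCEs and knowledge-testing) is voluntary and will not impact residents' performance in their program". Under Consent Procedures (Residents), "Completing the resident surveys will indicate consent to participate in the study". A research assistant enrols residents, after the program director has started recruitment and supplied e-mail addresses.

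**Analysis set.** Resident Recruitment limits the intention-to-treat analysis to enrolled residents, whatever their attendance at live modules. Residents who decline are outside it.

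**Instruments.** The resident tests are "validated instruments that assess knowledge, attitudes, and self-reported skills on a Likert-type scale". The OSCE is scored by a standardized patient and an observer described as impartial. Masking to arm is not mentioned for anyone.

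**Comparison affected.** SAP Table 7 powers the Early-versus-Delayed comparison on the post-test proportion 'adequate', 50% against 65.5%, with 159 residents per group.

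**The concern.** Randomising sites makes the eligible residents comparable in expectation. It does not do so for those who volunteer afterwards, if the decision to volunteer can be influenced by the arm. A resident whose timetable already shows PACTS sessions and one whose site has been told to wait a year may differ in readiness to enrol. They may also rate their own attitudes and skills differently. The intention-to-treat statement deals with missed sessions, not with refusal.

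At stake is the Early-versus-Delayed contrast, the only randomised comparison among the resident analyses; the others are within-group. A gap in starting level would carry directly into the post-test comparison that Table 7 powers.

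**Working it through.** **1. Does enrolment follow allocation?** Baseline testing after randomisation is stated. Enrolment after randomisation is an inference: if completing the survey is the consent, nobody is enrolled before the first survey, and that survey comes after randomisation. The Protocol's expectation of enrolling 400 residents at the start of the study does not place enrolment before allocation.

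**2. Is the arm withheld?** Neither document says that it is kept from residents or recruiting research assistants until baseline is complete. Neither says when they learn it. The impartial OSCE observer bears on scoring, not on the decision to enrol or on self-report.

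**3. The plan's own figure.** Inputs from Table 7: p1 = 0.50, p2 = 0.655, 80% power, alpha 0.05 (taken as two-sided; the SAP does not say).

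n = [1.960 × √(2 × 0.5775 × 0.4225) + 0.842 × √(0.50 × 0.50 + 0.655 × 0.345)]² / 0.155² = (1.369 + 0.581)² / 0.0240 ≈ 158.2, rounded up to 159.

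This matches Table 7. The sample size is not in dispute; it supplies the yardstick of 65.5 − 50 = 15.5 points.

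**4. Illustration of selective enrolment.** Assume no true effect, 50% 'adequate' among eligible residents in both arms, and no selection in one arm. In the other, let a and b be the enrolment rates of 'adequate' and 'sub-optimal' residents. The observed share is a / (a + b). The rates are assumptions; neither document gives any.

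| a | b | Enrolled overall | Observed 'adequate' | False gap (points) |
|---|---|---|---|---|
| 90% | 80% | 85% | 0.90/1.70 = 52.9% | +2.9 |
| 80% | 90% | 85% | 0.80/1.70 = 47.1% | −2.9 |
| 80% | 70% | 75% | 0.80/1.50 = 53.3% | +3.3 |
| 95% | 75% | 85% | 0.95/1.70 = 55.9% | +5.9 |
| 80% | 60% | 70% | 0.80/1.40 = 57.1% | +7.1 |

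A 10-point difference in enrolment thus gives about 3 points, or 2.9/15.5 = 19% to 3.3/15.5 = 21% of the detectable difference.

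**5. Effect on the test.** At 159 per group the standard error under no difference is √(2 × 0.25/159) = 0.056. A false gap of 0.029 is 0.52 standard errors. The chance of a significant result in that direction rises from 2.5% to about 1 − Φ(1.96 − 0.52) ≈ 8%, ignoring clustering.

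**6. Which rows fit the plan?** The Protocol expects 50 enrolled per site from programs of 46 to 72 residents. With 85% enrolled, 50 per site needs a mean program size of 50/0.85 = 58.8, near the range midpoint of 59 (the true mean is not given). With 70% enrolled it needs 50/0.70 = 71.4, almost the maximum. At a mean of 59, four sites would then yield 4 × 59 × 0.70 ≈ 165 residents, not 200.

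**The case against.** Several points on the other side stand.

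- **Incentive.** All residents receive PACTS whether or not they enrol, so enrolling brings no training in either arm. The SAP uses three time points for both groups, and Early residents return for retention testing, so the testing burden is similar. A reader might infer that Delayed residents have a clear reason to refuse. The documents do not show that.
- **Open label.** A reader might take the trial as declared open-label, with residents approached once they know their arm. Neither is stated. What is shown is that nothing prevents it, and a timetabled compulsory curriculum is hard to hide at Early sites.
- **Room for refusal.** The Protocol attributes the expected 50 per site partly to away rotations. The whole difference between program size and enrolment cannot be read as refusal, and the 7-point row needs programs near the maximum size.
- **Consent after teaching.** The Protocol also says "Following the didactic curriculum and prior to the first testing sessions, residents will review an informational sheet that they may keep for reference". A reader might conclude that Early residents decide after being taught. But the baseline OSCE is "administered immediately before the intervention", and Research Design and Methods also puts testing before the curriculum. These passages conflict and must be reconciled; the stronger reading is not established.
- **Required or voluntary.** The statement "Residents will be required to take a knowledge survey before and after receiving the PACTS curriculum or standard training" conflicts with voluntary participation, but it covers both arms, so it is no evidence of arm-dependent recruitment.
- **Mitigations.** Programs are matched on size and patient diversity, a research assistant rather than the program director takes consent, and the SAP describes pre-post differences and models with resident and program factors. These reduce the effect of a baseline gap. They do not remove it: the baseline score is not named as a covariate, Table 7 powers a post-test comparison, and a self-rating given with knowledge of the arm is itself affected.

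**Conclusion.** The concern holds as a risk built into the sequence: allocation, then a voluntary baseline that is also the consent, then analysis of enrolled residents only, with no stated withholding of the arm. The documents do not show that bias has occurred, and fix neither its direction nor its size; it could favour PACTS or run against it. About 3 points against 15.5 is a reasonable illustration. It rests on an assumed 10-point difference in enrolment in one arm, none in the other, a 50% true share and no allowance for clustering. Larger gaps need stronger assumptions and, for the 7-point case, fit poorly with the plan's own enrolment numbers. The risk of influenced answers concerns the self-reported measures most. The risk of selective enrolment reaches every resident outcome.

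**What to change.** 1. **Protocol, Research Design and Methods and Consent Procedures (Residents).** State that residents at all eight sites receive the information sheet and complete the baseline survey, which is the consent, in one common window before the site's arm is disclosed to residents and to the research assistants who recruit them. Leave the OSCE at its stated time. This also settles the conflict over when the information sheet is given.
2. **SAP, Between-group differences.** Name the baseline score as a covariate in the Early-versus-Delayed models.
3. **Reporting.** Give eligible, approached and enrolled residents by site and arm.
4. **Separate wording point.** Reconcile the required knowledge survey with the voluntary participation stated under Resident Recruitment and in the answer on subject safety.

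**Cost.** Calendar co-ordination across eight sites and possibly a short wait at Early sites. Program directors must know the timetable in order to book sessions, so some leakage remains possible. The Protocol already refers to current participants, so some residents may be enrolled. For them the common window comes too late, but items 2 and 3 still apply.

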To evaluate patients' satisfaction and clinical quality related to PACTS training, we will employ research assistants to administer surveys to patients treated by residents to determine satisfaction with pain management, communication, trust-building, and comprehension of the informed consent discussion two months before and after the intervention is implemented. Patient satisfaction will be assessed using elements of the validated Pain Treatment Satisfaction Scale (PTSS). Patients will complete this survey privately after a brief explanation and informed consent from the research assistant. Patients will be asked to provide their self-reported race/ethnicity. Finally, clinical surgical outcomes obtained from the NSQIP database and/or electronic health record will be assessed for each patient participant before and after the PACTS curriculum is implemented to measure individual outcomes such as length of stay, postoperative complications, unplanned reoperations, and 30-day morbidity/mortality. The survey will be translated into 5 additional languages (Spanish, Portuguese, Haitian Creole, Simplified Chinese, and Traditional Chinese) in order to ensure a representative patient sample from diverse groups of patients. This survey will be piloted (N=10) from Partners sites using a convenience sampling method to assess the length of time required for survey completion and clarity of questions.

Resident Curriculum Impact Focus Groups

Due to the COVID-19 pandemic and increased focus on structural racism and equity in medicine, we believe that residents undergoing our curriculum may have had experiences that could provide further insight into providing equitable care. We believe that surgical residents who are receiving the curriculum would offer the best opportunity to gain insight regarding how the current curriculum content has impacted the care they provide their patients.

Focus group participants will be recruited from current PACTS participants. Two focus groups will be conducted at each PACTS site, with 8-10 participants in each focus group. Focus groups will be facilitated by study staff in a semi-structured focus group model.

PACTS Program/ Curriculum Evaluation

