Cover Page for ClinicalTrials.gov

Official Study Title:

Evaluation of a Cultural Dexterity Training Program for Surgeons: The PACTS Trial

NCT Number:

NCT03576495

Document:

Statistical Analysis Plan

Document Date:

June 6, 2017

PACTS ANALYSIS PLAN: The multi-year cluster-randomized study design will enable us to examine differences between and within the Early Intervention and Control/Delayed PACTS training groups across three unique time points (Year 2 pre-intervention, Year 2 post-intervention and Year 3 post-intervention). Details of statistical measures/methods and power calculations appear below.

Within-group differences (repeated measures).

Repeated measure differences on dichotomous outcomes will be examined using Chi-square and Fisher's exact tests, as well as unadjusted logistic regression models controlling for resident-specific demographic factors (e.g. age, IAT, post-graduate year, and sex).

Differences in ordinal outcomes (e.g. three- or five-point Likert scale reporting or ordered category scores) between pre- and post-intervention testing will be examined using Chi-square tests, unadjusted ordered logistic regression, and ordered logistic regression adjusted for resident- and program-specific factors. Table 7 depicts our sample size/power calculations, according to which we will be able to detect an 11% absolute difference in the proportion achieving "adequate" vs. "sub-optimal" dichotomized assessments before and after PACTS training. This accounts for an up to 20% sample loss from the expected 200 enrolled residents per group.

Between-group differences (independent measures). Pre- vs. post- differences in both self-reported and observer-assessed ordinal outcomes between the Early and Delayed Intervention groups will be assessed at the end of the first training period using Chi-square tests and unadjusted ordered logistic regression, as well as ordered logistic regression models controlling for resident- and program-specific factors. Previous work demonstrated that exposure to training similar to PACTS was associated with a 20-25% increase in the proportion of trainees achieving "adequate" scores on an OSCE-based assessment. Based on the number of residents in each arm (n=200), we anticipate that we will be able to detect a much smaller between-group difference even with up to 20% sample attrition over time (Table 7).

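### As planned, the Delayed arm's year-2 before/after analysis does not separate PACTS from further training, retesting and secular change

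*Protocol*

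**What the plan says.** The protocol's Research Design and Methods states the purpose as follows: "We will conduct a cross-over, cluster-randomized trial at 8 academic medical centers (AMCs) to capture the effect of PACTS on" resident, skills and patient outcomes. For the Delayed sites, "we will conduct baseline testing prior to the standard residency curriculum, and administer the PACTS curriculum the following year". The year-2 analysis of that arm is described as "within-group differences for the Delayed Intervention Group at the end of year 2". For the other arm, "we will also be able to test post-exposure effect retention in the Early Intervention Group at the end of year 2". So both arms have had PACTS by the end of year 2.

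The SAP names three test occasions: "Year 2 pre-intervention, Year 2 post-intervention and Year 3 post-intervention". I read its Year 2 as the protocol's first intervention year, and its Year 3 as the protocol's year 2. On that reading the Delayed arm's change over its PACTS year runs from the second occasion to the third. Its change from the first occasion to the second is a year without PACTS. The protocol's Residents section supports this: "Residents will be required to take a knowledge survey before and after receiving the PACTS curriculum or standard training".

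The SAP's within-group section uses chi-square, Fisher's exact and logistic or ordered logistic models, with post-graduate year among the example covariates. It says "we will be able to detect an 11% absolute difference in the proportion achieving" an adequate assessment before and after training, and Table 7 gives 160 residents measured twice, 50% to 61%. The between-group section places its comparison after the first training period only. Table 7 gives that comparison 159 per arm, 50% to 65.5%.

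**The concern.** In year 1 the Delayed arm is an unexposed concurrent control. In year 2 there is none. The Delayed arm's change then contains PACTS, a further stretch of residency, a further round of testing, and whatever changed in the environment. The plan lists no term for period or test occasion and specifies no year-2 between-arm analysis in its detailed methods.

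The protocol recognises that the environment was changing. It introduces extra focus groups with the words "Due to the COVID-19 pandemic and increased focus on structural racism and equity in medicine", and it allows the OSCE to move to video. The SAP, dated June 2017, provides for neither.

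At stake is whether ordinary progress could be read as benefit from the curriculum. The uncontrolled comparison also has the more favourable detectable difference in Table 7 (11 points against 15.5).

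**Working it through.** **1. What each comparison contains.** Let a_E and a_D be the arms' baseline levels, p2 and p3 the natural shifts from baseline at occasions 2 and 3 (training, retesting and secular change together), j the effect just after PACTS, and o the effect one year after.

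| | Occasion 1 | Occasion 2 | Occasion 3 |
|---|---|---|---|
| Early | a_E | a_E + p2 + j | a_E + p3 + o |
| Delayed | a_D | a_D + p2 | a_D + p3 + j |

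- Year-1 randomised contrast of changes: (p2 + j) − p2 = j.
- Delayed year-2 change: (p3 − p2) + j. The bias equals the natural change p3 − p2.
- Delayed standard-year change: p2. Subtracting it removes the bias only if p3 − p2 = p2, that is, if drift is the same in both years.
- Year-2 Early minus Delayed, net of baseline: o − j. This is retention only if j is the same in both years.

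Six means are fitted by six quantities, so j is determined by year 1. The Delayed year-2 change informs the period shift.

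**2. Reproducing Table 7** (two-sided 0.05 assumed; power 80%).

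- Within-group: n = [(1.96 × √(0.5 × 0.5) + 0.8416 × √(0.61 × 0.39)) / 0.11]² = 159.8, so 160. This is a test against a fixed 50%. A McNemar calculation with discordance 0.25 gives the same number, because 0.25 − 0.11² = 0.2379 = 0.61 × 0.39. The documents state neither method nor discordance. Neither route allows for natural change.
- Attrition: 200 × 0.8 = 160.
- Between-group: n = [1.96 × √(2 × 0.5775 × 0.4225) + 0.8416 × √(0.5 × 0.5 + 0.655 × 0.345)]² / 0.155² = 158.2, so 159. The row assumes that the untrained arm stays at 50%.

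**3. Chance of a significant result with zero PACTS effect** (n = 160, discordance 0.25, baseline 50%; natural gain d assumed).

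Paired test: Φ[(d√n − 1.96√0.25) / √(0.25 − d²)], plus the negligible opposite tail. For d = 0.05: (0.632 − 0.980) / 0.497 = −0.70, giving 0.24.

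Unpaired chi-square on the same pairs: the critical difference is 1.96 × √(2p̄(1 − p̄)/160), with p̄ the mean of the two rates, and the true SE is √((0.25 − d²)/160). For d = 0.05: (0.0500 − 0.1094) / 0.0393 = −1.51, giving 0.07.

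| Natural gain | Paired | Unpaired chi-square |
|---|---|---|
| 3 points | 12% | 2% |
| 5 points | 24% | 7% |
| 10 points | 72% | about 40% |

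For pre/post correlations of 0.3 to 0.7, the paired figure at 5 points ranges from 19% to 37%. The unpaired test rejects less often because it ignores the pairing and overstates the SE. The bias in the estimate is the same under either test.

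**The case against.** Several stronger readings are tempting, and the documents do not support them.

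- *That the plan declares the Delayed year-2 change to be a PACTS effect.* The sentence speaks only of differences. Hypothesis 1 is comparative, and the randomised contrast has its own paragraph and power row. Paragraph order in the SAP is not a ranking, and nothing shows which result will be emphasised.
- *That the 11-point row belongs to this comparison.* It covers within-group tests in general, in either arm.
- *That PACTS cannot be separated at all.* The limit lies in the planned analysis. The Delayed arm's standard-year change and the Early arm's year-2 change both give partial information. Post-graduate year is a listed covariate, though the SAP does not say whether it is updated, and it does not address retesting or calendar time.
- *That the SAP ignores the year-2 between-arm contrast.* Its opening promises differences between and within groups over all three occasions. The gap is that no method follows for the last one.
- *That year-2 Early minus Delayed is decay by randomisation.* It also needs an equal immediate effect in both years, which a move to a virtual OSCE or more senior residents could upset.
- *That year 2 fell in the pandemic.* The documents do not date year 2. The overlap is inferred from the September 2020 protocol version.

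The interval is also not fully settled, since the protocol places the OSCE just before the intervention and again 1 to 6 months after. Finally, the SAP names chi-square and logistic methods rather than McNemar, so the higher rejection rates depend on a paired test being used. These points narrow the concern. They leave an uncontrolled comparison with no planned adjustment for time or retesting.

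**Conclusion.** The concern holds for the planned analysis of the Delayed arm in year 2, and only there. Its estimate is off by the full amount of any natural change. How often that yields a significant result depends on the test: roughly 12%, 24% and 72% for gains of 3, 5 and 10 points if paired, and 2%, 7% and 40% if unpaired. The gain sizes and the discordance of 0.25 are assumptions, and clustering by the eight sites is ignored throughout. The year-1 randomised contrast does not depend on this comparison and is unaffected. The SAP should be changed, but the trial's main comparison is not undermined.

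**What to change.** - State that the effectiveness claim rests on the year-1 Early-versus-Delayed contrast, adjusted for baseline.
- Prespecify one model over all three occasions with site, period and exposure state (none, just trained, one year after). Residents share the same occasions, so the period term also takes up retesting.
- Report the Delayed year-2 before/after change as supportive or descriptive, beside that arm's own standard-year change.
- If the year-2 Early-versus-Delayed contrast is used for retention, state the assumption that the immediate PACTS effect is the same in both years.

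This needs SAP wording and some modelling on data already planned. The cost is precision: the 11-point figure no longer supports the effectiveness claim, and 15.5 points applies. Formally subtracting the standard-year change costs more. With correlation 0.5 across occasions, variance 0.25 and 160 residents, a single change has variance 2 × 0.25 × 0.5 = 0.25 and a detectable difference of 2.80 × √(0.25/160) = 11.1 points. The difference of the two yearly changes has variance 6 × 0.25 × 0.5 = 0.75, hence 2.80 × √(0.75/160) = 19.2 points. That is why it is better shown descriptively than tested.
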